 5. ESR
 6. CRP
 7. Hep B sAg, Hep C Ab, HIV ½ (if not performed in the previous 12 months prior to screening and only at enrollment)
 8. Immunoglobulin levels
 9. Flow cytometric analysis of peripheral B and T cells
 10. Urinalysis
 11. Urine human chorionic gonadotropin (hCG) in women of child bearing potential
 - xi. Quality of life surveys SF36 v2 and EQ 5D-5L
 - xii. Baseline ECG
 - xiii. Cough assessment/scale
4. Study Visits 2-16: Study visit 2 will occur at the 6 month time point from Day "0" (+/- 14 days) and subsequent visits will take place every three months (+/- 14 days) thereafter until a common close out date of 36 months after the last subject is enrolled.
 - a. Subjects will be seen every three months in clinic and the same measurements will be performed as listed in the Enrollment and Randomization Visit.
 - i. The VDI Score will only be calculated every other visit after Study visit 2 as this score is designed to measure cumulative damage every six months.
 - ii. Subject quality of life assessments SF 36v2 and EQ-5D-5L will be assessed every 6 months from time of Study visit 2.

- iii. ECG will be performed every 12 mos
- iv. Adverse Events will be assessed at each visit
- v. Cough assessment/scale
- b. In cases where subjects need to come in for an infusion in between scheduled visits, the visit directly after the infusion may be done over the phone instead of coming in to the clinic. This will be decided at the discretion of the PI based on any hardships the patients may have related to distance of travel. The same measurements will be performed as an on-site visit (VDI score, BVAS, adverse events, and cough/assessment), except for the ECG and blood draw. The ECG will be added to the next office visit, and blood work will be deferred for that visit, and resumed at the next time point. Subject Quality of Life Assessments SF36v2 and EQ-5D-5L may be mailed to subjects for completion, then returned at the next office visit.
- c. If subjects miss their scheduled visits and are unable to reschedule in window, a deviation will be filed and an investigator will call them to assess AEs and disease activity.
- d. Subject visits can be completed as telemedicine with remote lab draws during the COVID-19 pandemic. Lab draws may be delayed up to 4 weeks at the investigator's discretion. A minor deviation will be filed if lab draws occur outside that window.

B. Drugs to be used

Rituximab (Rituxan, Genentech), which is FDA-approved for GPA and MPA, will be used in the study.

C. Devices to be used

Not applicable

D. Procedures/surgical interventions

Not applicable

E. Data to be collected and when the data is to be collected

At present, there is no standard of care for maintenance of remission in ANCA vasculitis beyond the two-year mark; thus, the role of continuous versus intermittent B cell depletion requires investigation. Efficacy and toxicity are the foci of our outcome analysis for this study and will be assessed through analysis of primary and secondary endpoints.

The following variables will be collected at EACH study visit:

1. VDI (every 6 months)
2. Modified BVAS/WG
3. Laboratory data at baseline and at subsequent visits
 - a. Complete Blood Count
 - b. Comprehensive Metabolic Panel
 - c. eGFR
 - d. ANCA titer
 - e. ESR
 - f. CRP

- g. Immunoglobulin levels (every 6 months)
 - h. Urinalysis
 - i. Urine Hcg for women of child bearing potential (only at screening and when reinfused with rituximab)
 - j. Flow cytometric analysis of peripheral B and T lymphocyte markers
4. Concomitant medications at each visit
 5. Adverse events assessment

VI. Biostatistical Analysis

A. Specific data variables being collected for the study (e.g. data collection sheets)

Data variables collected are listed above and we will also verify contact information at each visit to ensure appropriate follow-up.

B. Study endpoints

Primary endpoints:

1. Disease flare defined as a BVAS/WG ≥ 2 . A subgroup analysis will be performed by ANCA subtype.

Secondary endpoints:

1. Proportion of patients with serious adverse events (SAEs), including all episodes of Late Onset Neutropenia (LON, absolute neutrophil count < 1000 cells/mm³)
2. The composite of disease flare (defined as BVAS/WG ≥ 2) and serious adverse events.
3. Total rituximab utilization during the study period
4. Accrued organ damage as assessed by the Vasculitis Damage Index (VDI)
5. Patient quality of life assessment using the SF-36v2 and EQ-5D-5L surveys every 6 months
6. Number of major (modified BVAS-WG ≥ 3) relapses
7. Survival
8. Hypogammaglobulinemia (IgG < 400 mg/dL)
9. All infections

C. Statistical methods

Data will be analyzed by the intention-to-treat principle. Randomization will be stratified on ANCA subtype (MPO vs PR3) and rituximab vintage (< 3 years vs > 3 years). Rituximab vintage is the duration of continuous rituximab therapy administered prior to enrollment in the study. We have contracted with the company StudyTRAX to perform randomization on stratified variables via random permuted blocks.

Continuous data will be summarized using descriptive statistics. Continuous data will be assessed using the t-test or Wilcoxon rank-sum test as appropriate. Categorical data will be assessed using the Chi-square and the Fisher exact tests as appropriate. The probability of remaining free of relapse will be estimated using the Kaplan-Meier method. The difference between the two

treatment strategies will be assessed using the log-rank test. *P* values of 0.05 will be considered significant.

D. Power analysis

Using a two-sided logrank test with an alpha level of 0.05, a projected relapse risk of 15% in the superior group and 30% in the inferior group, and an estimated enrollment time of 36 months, it was determined that 180 patients are required to detect a significant difference with a power of 0.80. We aim to enroll 200 patients in the study.

VII. Risks and Discomforts

Subjects may experience side effects while receiving rituximab, which is given as part of their regular medical care for their GPA or MPA. As per the entry criteria, subjects have been on rituximab for 2 years prior to enrollment, the side effects have been discussed in detail and a signed consent for rituximab is obtained for every patient receiving rituximab at the first dose and annually thereafter.

The effects of rituximab on a fetus are unknown and may be harmful. Individuals of childbearing potential should use effective birth control during treatment and for 12 months after their last rituximab infusion. Prior to any infusion of rituximab to a woman of childbearing potential, a urine pregnancy test is performed and recorded. If a woman is found to be pregnant, she will then be removed from the study and followed based on best medical judgment as deemed appropriate by the clinician investigator.

A. Complications of surgical and non-surgical procedures

Not applicable

B. Drug side effects and toxicities

Common side effects of Rituxan

- Infusion reactions may be fatal. Serious infusion reaction with hives, low blood pressure, breathing difficulties, irregular heartbeat and chest pain are very rare. Medications given as pre medication: Benadryl 25mg PO, tylenol 650mg PO and Solucortef 100mg IV, are always given and can prevent these reactions. We will temporarily stop the infusion immediately if a reaction occurs.
- Within 24 hours of the 1st infusion
 - Chills, itching, hives, sneezing, throat irritation
 - “flu like” symptoms: headache, nausea, joint pain
- Possible serious side effects or reactions that can occur at any time
 - Infections are a concern with all drugs that affect the immune system. If you develop a severe infection, we will check your labs including a complete blood count. This is always something that needs attention and treatment
 - Reactivation (getting symptoms again) of Hepatitis B and other viral infections. Hepatitis B Core is always checked at the screening or first visit.

- Worsening of asthma symptoms
- A rare brain infection, progressive multifocal leukoencephalopathy (PML), has been reported in people taking this medication. This infection is rare, associated with weakened immune systems, and can lead to death or severe disability.
- Skin reactions, painful sores, ulcers, blisters and peeling skin (rare)

There may be other risks of rituximab that are currently unknown.

As with any drug, the major possible side effect of rituximab can be an allergic reaction. Allergic reactions can be mild or more serious, and can even result in death.

Subjects cannot receive a live vaccine such as zostavax while receiving rituximab.

C. Risk of relapse

The discontinuation of maintenance rituximab will likely lead to an increase in disease relapse. Relapses have the potential to cause irreversible organ damage, resulting in significant morbidity. Particularly concerning is the potential for recurrence of rapidly progressive glomerulonephritis leading to ESRD and dialysis dependence. The risk of relapse must be weighed against the harms of ongoing treatment with immunosuppression. While no randomized clinical trials have been performed, standard of care is to continue maintenance therapy for 1-2 years. To mitigate the risk of significant morbidity from disease relapse, we have restricted entry to patients treated with maintenance therapy for a minimum of 2 years and excluded patients with an eGFR < 20 ml/min/1.73 m².

D. Device complications/malfunctions

Not applicable

E. Psychosocial (non-medical) risks

There are no known psychosocial risks associated with this study, however there may be unknown risks that will be addressed if they become known.

F. Radiations Risks

Not applicable

VIII. Potential Benefits

A. Potential benefits to participating individuals

There may not be any direct benefits to subjects who participate in this trial. Information learned by conducting this trial may benefit future patients by helping determine a long term plan with regards to rituximab administration for patients with GPA or MPA.

B. Potential benefits to society

This study, once completed, will be a landmark trial in the field of remission maintenance therapy for ANCA vasculitis. Currently, specialists do not know the ideal treatment strategy for this subset of patients and this study is likely to provide the answer. In addition, if it is found that either Arm 1 or Arm 2 are as effective as ongoing continuous therapy, there will be cost-effective benefit to society in that less rituximab will be required to maintain remission.

IX. Monitoring Quality and Assurance

A. Independent monitoring of source data

The PI on this study will be responsible for the data management, integrity of this data and adherence to the IRB-approved protocol. The PI will review the accuracy and completeness of entries, source documents, and informed consent on a regular basis.

Privacy of subjects will be protected and confidentiality of data collected maintained. All individually identifiable information will be stored in a secure, locked, location in the PI's office. Password-protected computer databases will be used with limited access to the study data. Files for data analysis will contain codes instead of identifiers. All identifiers will be removed once study is completed.

B. Safety monitoring

The patient's treating physician will be responsible for the treatment of any adverse events, in accordance with the approved product labeling and the physician's discretion.

Subjects will be withdrawn from the study at any point for the following reasons:

1. Serum IgG < 250 mg/dL at any point during the study.
2. Modified BVAS-WG ≥ 2
3. Require daily prednisone >7.5mg

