5. Treated with continuous rituximab at regularly scheduled intervals with a goal of undetectable B cells for at least 24 months.
6. In sustained remission (defined by a modified BVAS-WG=0 **AND** a prednisone dose of \leq 7.5mg for at least 12 months).
7. Undetectable (<10mm³) B cells as quantified by the number of CD20+ cells on peripheral blood flow cytometry on day 0.
8. Urine Hcg negative for women of child bearing potential and not planning to become pregnant for at least 12 months from enrollment and at least 12 months after any study related rituximab dose
9. Judged to be otherwise healthy by the Investigator, based on medical history and physical examination (no known active disease process for which life expectancy is less than 36 months)

Exclusion criteria:

1. Secondary Disease: disease suspected to be induced by levamisole-adulterated cocaine
2. All transplanted patients
3. Treatment: additional immunosuppressive agents other than rituximab and/or total daily prednisone dose \geq 7.5 milligrams
4. Hypogammaglobulinemia: IgG level < 300mg/dL
5. Terminal cancer or other primary illness with life expectancy of less than 36 months
6. Active anti-GBM disease and other known autoimmune disease for which the need for additional immunosuppression is likely
7. Pregnancy or breastfeeding

B. Sources of subjects and recruitment methods

Subjects will be recruited from the current pool of patients in the MGH Renal and Rheumatology Units of the Vasculitis and Glomerulonephritis Center.

IV. Subject Enrollment

A. Methods of enrollment

Patients will be prescreened for eligibility by research staff prior to their scheduled rituximab infusion. Potential subjects will be assessed for eligibility utilizing existing data regarding current length of treatment with rituximab, prednisone dose (if any) and most recent Birmingham Vasculitis Activity Score.

At a regularly scheduled clinic visit, study site personnel will assess a patient's eligibility for enrollment, including review of the inclusion and exclusion criteria. Patients meeting all the inclusion criteria and have no exclusionary criteria and receive treatment for their ANCA Associated Vasculitis by physicians in the MGH Renal and Rheumatology Unit's Vasculitis and Glomerulonephritis Center will be offered the opportunity to participate in this study as part of their ongoing treatment.

B. Procedures for obtaining informed consent

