4. WBC <3,000
5. Serious Infections that require hospitalization.

The investigators will also review the data every 6 months to ensure there are no safety concerns or clear inferiority in one arm that would warrant early termination of the trial.

C. Outcomes monitoring

The following outcomes will be collected throughout the study period as appropriate:

1. Disease flare defined as a BVAS/WG ≥ 2 (**primary aim**). A subgroup analysis will be performed by ANCA subtype.
2. Proportion of patients with serious adverse events (SAEs), including all episodes of LON.
3. Number of infections (mild and severe).
4. Total rituximab utilization during the study period.

5. Patient quality of life assessment using the SF-36v2 and EQ-5D-5L surveys every 6 months
6. Number of major (modified BVAS-WG ≥ 3) relapses
7. Survival
8. Hypogammaglobulinemia (IgG < 400 mg/dL)

D. Adverse event reporting guidelines

All adverse events will be reported per PHRC guidelines which includes unanticipated problems involving risks to subjects/others, including adverse events, within 5 working days/7 calendar days of the date that the investigator first became aware of the problem.

References

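### Secondary endpoint 8 (IgG below 400 mg/dL) can already be met at entry, and the plan gives quality of life an unadjusted test without saying whether level or change is compared

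*Combined protocol and SAP*

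**What the plan says.** **IgG.** Section VI.B lists secondary endpoint 8 as "Hypogammaglobulinemia (IgG < 400 mg/dL"). Section IX.C repeats it under the lead-in "The following outcomes will be collected throughout the study period as appropriate". Exclusion criterion 4 in section III.A reads "Hypogammaglobulinemia: IgG level < 300mg/dL". Section IX.B opens its withdrawal list with "Subjects will be withdrawn from the study at any point for the following reasons", and the IgG item there is "Serum IgG < 250 mg/dL at any point during the study". Immunoglobulins are on the Study Visit 1 blood list in section V.A and in the follow-up schedule in section V.E: "Immunoglobulin levels (every 6 months").

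**Quality of life and VDI.** SF-36v2, EQ-5D-5L and the Vasculitis Damage Index are all collected at Study Visit 1 (section V.A). Secondary endpoint 5 names the two surveys and their six-monthly schedule, but no score, time point or form of comparison. Secondary endpoint 4 describes organ damage as accrued.

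**Tests.** Section VI.C gives one sentence for each type of data: "Continuous data will be assessed using the t-test or Wilcoxon rank-sum test as appropriate" and "Categorical data will be assessed using the Chi-square and the Fisher exact tests as appropriate". It mentions no covariate and does not say whether a continuous outcome enters as a follow-up value or as a change. Randomization is stratified on ANCA subtype and rituximab vintage.

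**The concern.** The three IgG cut-offs leave a gap. A patient who enters at 300-399 mg/dL is eligible, already satisfies endpoint 8, and is not removed by the IgG withdrawal rule unless the value falls below 250. Nothing restricts the endpoint to new cases, so two analysts could follow the plan and report different event counts from the same data. If entry cases count equally in both arms, they add the same number of events to each and pull the risk ratio toward 1.

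For quality of life, the choice between level and change is open, and which is more precise depends on a correlation that the documents do not give. Adjusting for the Visit 1 score avoids that dependence. The trial is open-label, so it is better to fix these choices before results by arm are seen.

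**Working it through.** The documents give no power figure for these endpoints, so there is none to reproduce. The 180 patients in section VI.D belong to the primary log-rank test and are not touched here.

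**Inputs.** From the documents: the IgG cut-offs 300, 400 and 250 mg/dL; planned enrolment of 200. Assumed: 1:1 allocation (100 per arm), two-sided 5% tests, the share q entering at 300-399, the onset rates, a 0.3 SD difference in quality of life, and the correlation r between Visit 1 and follow-up scores. The documents give none of these for the endpoints concerned.

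**1. IgG.** Let p be the risk of new onset among patients entering at 400 or above. If every entry case counts, the event proportion in an arm is q + (1 − q)p, and the arm difference shrinks by the factor (1 − q). If only new cases count, the proportions stay at p with 100(1 − q) patients per arm.

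At q = 10% and onset 5% vs 15%:
- everyone counted: 0.10 + 0.90 × 0.05 = 14.5%, against 0.10 + 0.90 × 0.15 = 23.5%; the risk ratio is 1.62 instead of 3.0
- new cases only: 5% vs 15% with 90 per arm

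Power, from the two-proportion formula with pooled variance under the null:

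| Onset | q | New cases only | Everyone counted |
|---|---|---|---|
| 5% vs 15% | 1% | 65% | 61% |
| 5% vs 15% | 2% | 65% | 58% |
| 5% vs 15% | 5% | 63% | 48% |
| 5% vs 15% | 10% | 61% | 37% |
| 10% vs 25% | 10% | 76% | 59% |
| 10% vs 20% | 10% | 47% | 32% |

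**2. When entry cases recover.** The table counts every entry case. Now let half of them count on average, at q = 10%. An arm's proportion is 0.10 × s + 0.90 × p, where s is the share of its entry cases that count. Low-onset arm first:

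| Onset | New cases only | s 50%/50% | s 40%/60% (same direction as onset) | s 60%/40% (opposite) |
|---|---|---|---|---|
| 5% vs 15% | 61.0% | 45% | 61.2% | 30% |
| 10% vs 25% | 75.9% | 66% | 77.5% | 52% |
| 10% vs 20% | 46.7% | 37% | 51.7% | 25% |

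In the same-direction column, counting everyone equals or beats the new-onset rule.

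**3. Quality of life.** Take equal variances at the two times and set the follow-up variance to 1. The residual variance is then 1 for a level test, 2(1 − r) for change and 1 − r² for ANCOVA. ANCOVA is never the largest: 1 − r² ≤ 1, and 2(1 − r) − (1 − r²) = (1 − r)² ≥ 0. Power from the non-central t distribution, 0.3 SD, 100 per arm:

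| r | Level | Change | ANCOVA |
|---|---|---|---|
| 0.3 | 56% | 43% | 60% |
| 0.5 | 56% | 56% | 68% |
| 0.7 | 56% | 78% | 84% |
| 0.8 | 56% | 92% | 94% |

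Below r = 0.5 change is worse than level; above it, better.

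**4. VDI.** The endpoint wording already indicates an increment. In a simulation with assumed accrual of 0.2 vs 0.4, 0.3 vs 0.6 and 0.5 vs 0.8 new items per patient (100 per arm, items never resolving), a t-test on change had 73%, 90% and 74% power, and ANCOVA 73%, 89% and 74%. Adjustment adds nothing.

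**The case against.** Four objections have force.

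- A reader might infer that the stated test ignores the Visit 1 scores. The documents do not support that: section VI.C names tests, not the variable tested, and a t-test on change uses Visit 1. What stands is the silence on level or change and the absence of adjustment.
- A reader might extend the precision loss to VDI. The word accrued points to change, and on change the stated t-test does as well as ANCOVA. No loss is claimed there.
- The IgG dilution is conditional. Both arms stop scheduled rituximab, so entry cases may recover, and recovery may differ by arm. If it differs in the same direction as onset, the new-onset rule can lose power: at 10% prevalence, 75.9% against 77.5%, and 46.7% against 51.7%. The rule also leaves out some randomized patients although section VI.C states intention-to-treat. This stands, and is why the binary analysis should not be reported alone.
- The stated tests are valid in randomized arms. At r = 0.8, ANCOVA gains only two points over change, and at 1-2% prevalence the IgG loss is a few points. That stands and bears on severity.

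**Conclusion.** The point holds as a minor one. Endpoint 8 is met on entry by anyone admitted at IgG 300-399, and the plan does not say how such patients count. If all of them count equally in both arms, the loss with onset 5% vs 15% is about 7 points of power at 2% prevalence and 24 points at 10%. The true share is not in the documents and could be small.

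For quality of life, ANCOVA has at least the precision of either t-test the plan could mean. At an assumed 0.3 SD and r from 0.3 to 0.8, its gain is 4 to 38 points over level (60 − 56 to 94 − 56) and 17 down to 2 points over change (60 − 43 to 94 − 92).

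A reader might take the entry cases for a source of bias. The documents do not support that, because randomization balances them on average; the harm is dilution. Endpoints 4, 5 and 8 lie outside the three secondary aims in section II, and the primary log-rank analysis is unaffected.

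**What to change.** - **Endpoint 8:** report first post-randomization IgG below 400 mg/dL among patients with Visit 1 IgG of 400 or above, by arm. Beside it, report continuous IgG adjusted for its Visit 1 value in all randomized patients. The second analysis is needed because the first omits patients who enter below 400 and can be the weaker one if their recovery differs by arm.
- **Quality of life:** name Visit 1 as baseline. Analyse SF-36v2 and EQ-5D-5L by ANCOVA or a mixed model with the Visit 1 value, arm, ANCA subtype and rituximab vintage, at a named time. The study design statement in section I already uses 18, 24 and 36 months.
- **VDI:** confirm that the quantity is change from Visit 1. This is a clarification only.

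The cost is a few sentences in section VI and routine programming. All the measurements are already scheduled.

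### IgG is measured repeatedly as a number but analysed only as below 400 mg/dL or not. Under a general shift this costs power, and some patients can enter already meeting the endpoint.

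*Combined protocol and SAP*

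**What the plan says.** The eighth of nine secondary endpoints in VI.B is "Hypogammaglobulinemia (IgG < 400 mg/dL". The outcomes list in IX.C repeats it. Neither list has mean IgG, change in IgG or slope. Endpoint 8 carries no time point and does not say whether it means ever, at the last visit, or newly below the cut.

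The level itself is collected. Immunoglobulins are in the Visit 1 blood work (V.A.3), and for later visits V.A.4 says "Subjects will be seen every three months in clinic and the same measurements will be performed as listed in the Enrollment and Randomization Visit". The data list in V.E gives "Immunoglobulin levels (every 6 months". The two lists differ in frequency, but every 6 months is the minimum on either reading.

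For analysis, VI.C says "Categorical data will be assessed using the Chi-square and the Fisher exact tests as appropriate". It also says "Continuous data will be assessed using the t-test or Wilcoxon rank-sum test as appropriate", without naming IgG.

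Two other IgG limits apply. The exclusion list in III.A has "Hypogammaglobulinemia: IgG level < 300mg/dL", and the withdrawal list in IX.B has "Serum IgG < 250 mg/dL at any point during the study".

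**The concern.** Cutting a continuous measure at one value discards information about everyone who is not near it. A fall from 1000 to 420 mg/dL is no event, while a fall from 420 to 390 mg/dL is one. If one strategy lowers IgG somewhat in most patients, the proportion below 400 mg/dL is a weak way to see it, and a non-significant result could be read as no difference in humoral toxicity. That matters because section I sets the risk of relapse against the risk of treatment-related harm, and V.E names efficacy and toxicity as the foci of the outcome analysis.

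The entry limit adds a second problem. Since only patients below 300 mg/dL are excluded, someone at 300 to 399 mg/dL meets the endpoint on the day of randomization. With no new-onset rule, such patients can be counted as events that the assigned strategy did not cause. Randomization spreads them evenly on average, so they dilute the comparison rather than bias it.

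**Working it through.** **The plan's own figure.** There is none for IgG: no mean, SD, prevalence, expected difference or power target. The only power statement (VI.D) concerns relapse: "Using a two-sided logrank test with an alpha level of 0.05, a projected relapse risk of 15% in the superior group", against 30% in the inferior group, 180 patients, power 0.80. It reproduces closely on one reading. HR = ln(0.85)/ln(0.70) = 0.456, and Freedman's formula gives 57 events. If the risks are 36-month risks, with 36 months of accrual and 36 more of follow-up, the mean event probability is 0.313 and N = 57/0.313 = 182. This has no bearing on IgG beyond supplying alpha and sample size.

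**Inputs.** From VI.D: two-sided 5%, and 180 to 200 patients. Assumed: 1:1 allocation (90 to 100 per arm), normally distributed IgG, a uniform shift of d SD between arms, and a prevalence p below 400 mg/dL at the midpoint between arms.

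**Formulas**
- Level: power = Φ(d/√(2/n) − 1.96).
- Cut: p1 = Φ(z − d/2) and p2 = Φ(z + d/2), with z = Φ⁻¹(p). Power = Φ((p2 − p1 − 1.96·SE0)/SE1), with SE0 pooled and SE1 unpooled.

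**Worked case: n = 100, d = 0.4, p = 10%**
- Level: 0.4/√0.02 = 2.828, and Φ(2.828 − 1.960) = 0.81.
- Cut: p1 = Φ(−1.482) = 0.069 and p2 = Φ(−1.082) = 0.140. SE0 = 0.0433 and SE1 = 0.0430. Φ((0.0705 − 0.0848)/0.0430) = Φ(−0.33) = 0.37.
- Loss: 44 points.
- If 10% is instead the prevalence in the better arm, the cut has 43% power and the loss is 38 points.

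**Power at 100 per arm (loss in points in brackets)**

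| Shift | Level | Cut, p = 5% | p = 10% | p = 20% | p = 30% |
|---|---|---|---|---|---|
| 0.2 SD | 29% | 10% (20) | 13% (17) | 16% (13) | 19% (11) |
| 0.3 SD | 56% | 17% (40) | 23% (33) | 31% (25) | 36% (20) |
| 0.4 SD | 81% | 26% (55) | 37% (44) | 50% (31) | 57% (24) |
| 0.5 SD | 94% | 37% (58) | 52% (42) | 68% (26) | 76% (18) |

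Including 90 per arm, the range is about 10 to 58 points.

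**Sensitivity**
- Prevalence outside 5 to 30%: at 2% the loss reaches 73 points; at 50% it is 9 to 20 points for shifts of 0.2 to 0.5 SD.
- Fisher's test in place of chi-square, p = 5%, d = 0.4: 16% against 81%, a loss of 65 points.
- Baseline IgG as covariate, assumed correlation 0.5, d = 0.4: power on the level rises from 81% to 90%.
- Simulated repeated values (assumed mean/SD 700/200, 800/250 and 600/150 mg/dL, entry at 300 or above, final shift 0.3 to 0.5 SD, 100 per arm), compared with a t-test on the last value: the loss is 38 to 54 points for ever below 400 and 31 to 48 for last value below 400.
- Effect in a subgroup only: if 10 to 15% of the worse arm fall by 2 to 3 SD and the rest do not change, with 5 or 10% below the cut otherwise, the result runs from a 1-point advantage for the level to a 15-point advantage for the cut.

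**Patients already below 400 at entry.** Under the same assumed distributions, the share of entrants at 300 to 399 mg/dL is [Φ((400 − mean)/SD) − Φ((300 − mean)/SD)] / [1 − Φ((300 − mean)/SD)]. For 700/200 this is (0.067 − 0.023)/0.977 = 4.5%; for 800/250 it is 3.3%; for 600/150 it is 7.0%.

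**The case against.** The strongest reply is that hypogammaglobulinemia is a threshold event. The protocol handles IgG by thresholds at entry and withdrawal, and a mean shift within a safe range answers a different question. This stands, and together with the subgroup result it is why the cut should stay as a reported comparison.

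The generic sentence on continuous data in VI.C would also permit a test of the level. That is true, but it names no IgG variable, time point or baseline adjustment, so it permits an analysis without planning one.

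Withdrawal is a fair objection to the power figures, which assume that every patient contributes. IX.B withdraws patients for relapse, low IgG and other events. If 30% had no value (an assumption, leaving 70 per arm), power on the level at 0.4 SD falls to about 66%. The cut at 10% prevalence falls too: both standard errors grow by √(100/70) = 1.195, giving Φ((0.0705 − 1.96 × 0.0517)/0.0514) = 27%. The gap is still about 39 points.

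A reader might infer several stronger things that the documents do not support:
- That IgG is the only toxicity measure recorded as a number. Blood counts and flow cytometry are too, and they are listed for each visit.
- That the arms are expected to differ in rituximab exposure. Secondary Aim 3 poses this as a question.
- That the repeated values are discarded. With no time rule, an ever-below-400 reading would use them all, though still only as yes/no.

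**Conclusion.** The point holds in conditional form. The only planned IgG outcome is a yes/no cut on a level that is measured repeatedly. Under a general shift of 0.2 to 0.5 SD, with 5 to 30% of patients below 400 mg/dL and 90 to 100 per arm, the cut costs roughly 10 to 60 points of power by the chi-square test. Every IgG input there is an assumption. It would be wrong to read the range as a fixed property of this plan, because an effect confined to a small subgroup removes or reverses the loss.

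The entry problem needs no distributional assumption: the 300 mg/dL limit and the 400 mg/dL endpoint overlap, and no new-onset rule separates them. Only the 3 to 7% figure for its size is assumed.

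The importance is moderate. This is one secondary endpoint among nine with no stated power target. Infections, serious adverse events and rituximab use are compared as well, and the primary analysis and sample size are untouched.

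**What to change.** In VI.B and VI.C:

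1. Keep the proportion with IgG below 400 mg/dL. Define it as new onset among patients at or above 400 mg/dL at Visit 1, and report it by arm with a 95% CI.
2. Add a between-arm analysis of the IgG level: a mixed model on the 6-monthly values through 36 months from enrollment, with Visit 1 IgG, arm, visit, arm-by-visit, ANCA subtype and rituximab vintage as terms. Log-transform IgG if it is skewed. Report the adjusted difference at 36 months with its 95% CI.
3. State that values up to withdrawal enter the model, including any IgG value that triggers it.

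The cost is protocol wording and one model on data already collected, with no added visits, tests or patients. The downsides are one more secondary analysis, and a mean difference that is less direct clinically than the threshold it sits beside.
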